## **10. Data Recording**

### **10.1 Institutional Review Board (IRB) Approval and Consent**

It is expected that the IRB will have the proper representation and function in accordance with federally mandated regulations. The IRB should approve the consent form and protocol.

In obtaining and documenting informed consent, the investigator should comply with the applicable regulatory requirement(s), and should adhere to Good Clinical Practice (GCP) and to ethical principles that have their origin in the Declaration of Helsinki.

Before recruitment and enrollment onto this study, the patient will be given a full explanation of the study and will be given the opportunity to review the consent form. Each consent form must include all the relevant elements currently required by the FDA Regulations and local or state regulations. Once this essential information has been provided to the patient and the investigator is assured that the patient understands the implications of participating in the study, the patient will be asked to give consent to participate in the study by signing an IRB-approved consent form.

### **10.2 Adherence to the Protocol**

Except for an emergency situation in which proper care for the protection, safety, and well-being of the study patient requires alternative treatment, the study shall be conducted exactly as described in the approved protocol.

### **10.3 Record Retention**

Study documentation includes all eCRFs, data correction forms or queries, source documents, Sponsor-Investigator correspondence, monitoring logs/letters, and regulatory documents (e.g., protocol and amendments, IRB correspondence and approval, signed

patient consent forms).

Source documents include all recordings of observations or notations of clinical activities and all reports and records necessary for the evaluation and reconstruction of the clinical research study.

Government agency regulations and directives require that all study documentation pertaining to the conduct of a clinical trial must be retained by the study investigator. In all other cases, study documents should be kept on file until three years after the completion and final study report of this investigational study.

#### **10.4 Obligations of Investigators**

The Principal Investigator is responsible for the conduct of the clinical trial at the site in accordance with Title 21 of the Code of Federal Regulations and/or the Declaration of Helsinki. The Principal Investigator is responsible for personally overseeing the treatment of all study patients. The Principal Investigator must assure that all study site personnel, including sub-investigators and other study staff members, adhere to the study protocol and all FDA/GCP/NCI regulations and guidelines regarding clinical trials both during and after study completion.

### **11. Ethical and Legal Aspects**

#### **11.1 Ethical and Legal Conduct of the Study**

The procedures set out in this protocol, pertaining to the conduct, evaluation, and documentation of this study, are designed to ensure that the investigator abide by Good Clinical Practice (GCP) guidelines and under the guiding principles detailed in the Declaration of Helsinki. The study will also be carried out in keeping with applicable local law(s) and regulation(s).

Strict adherence to all specifications laid down in this protocol is required for all aspects of study conduct; the investigator may not modify or alter the procedures described in this protocol.

Modifications to the study protocol will not be implemented by the investigator without discussion and agreement by Janssen Scientific Affairs, LLC. However, the investigator may implement a deviation from, or a change of, the protocol to eliminate an immediate hazard(s) to the trial subjects without prior IEC/IRB/Janssen approval/favorable opinion. As soon as possible, the implemented deviation or change, the reasons for it and, if appropriate, the proposed protocol amendment should be submitted to the IEC/IRB/head of medical institution. Any deviations from the protocol must be explained and documented by the investigator.

The Principal Investigator is responsible for the conduct of the clinical trial at the site in accordance with Title 21 of the Code of Federal Regulations and/or the Declaration of Helsinki. The Principal Investigator is responsible for personally overseeing the treatment of all study patients. The Principal Investigator must assure that all study site personnel, including sub-investigators and other study staff members, adhere to the study protocol and all FDA/GCP/NCI regulations and guidelines regarding clinical trials both during and after study completion.

The Principal Investigator will be responsible for assuring that all the required data will be collected and properly documented.

## 11.2 Subject Information and Consent

Each subject/legal representative or proxy consentor will have ample time and opportunity to ask questions and will be informed about the right to withdraw from the study at any time without any disadvantage and without having to provide reasons for this decision.

Only if the subject/legal representative or proxy consentor voluntarily agrees to sign the informed consent form and has done so, may he/she enter the study. Additionally, the investigator and other information provider (if any) will personally sign and date the form. The subject/legal representative or proxy consentor will receive a copy of the signed and dated form.

The signed informed consent statement is to remain in the investigator site file or, if locally required, in the patient's note/file of the medical institution.

In the event that informed consent is obtained on the date that baseline study procedures are performed, the study record or subject's clinical record must clearly show that informed consent was obtained prior to these procedures.

1. If the patient is not capable of providing a signature, a verbal statement of consent can also be given in the presence of an impartial witness (independent of Janssen/Merck, and the investigator). This is to be documented by a signature from the informing physician as well as by a signature from the witness.
2. For adults under legal protection, consent shall be given by the legal guardian(s). The consent of an adult under legal protection shall also be requested where such a person is able to express his/her own will. His/her refusal or the withdrawal of his/her consent may not be disregarded.
3. In emergency situations, when prior consent of the patient is not possible, the consent of the patient's legal representative(s) or proxy consentor, if present, should be requested. The patient should be informed about the study as soon as possible and his/her consent to continue the study should be requested.

The informed consent form and any other written information provided to subjects/legal representatives or proxy consentors will be revised whenever important new information becomes available that may be relevant to the subject's consent, or there is an amendment to the protocol that necessitates a change to the content of the subject information and/or the written informed consent form. The investigator will inform the subject/legal representative or proxy consentor of changes in a timely manner and will ask the subject to confirm his/her participation in the study by signing the revised informed consent form. Any revised written informed consent form and written information must receive the IEC/IRB's approval/favorable opinion in advance of use.

## 11.3 Confidentiality

All records identifying the subject will be kept confidential and, to the extent permitted by the applicable laws and/or regulations, will not be made publicly available.

Should direct access to medical records require a waiver or authorization separate from the subject's statement of informed consent, it is the responsibility of the Investigator to obtain such permission in writing from the appropriate individual.

[Redacted]

[Redacted]

[Redacted]

[Redacted]

[REDACTED]

[REDACTED]

[REDACTED]

[REDACTED]

#### 12.4 Flow cytometry

The isolated peripheral blood mononuclear cells before, during and after treatment will be analyzed to measure the frequency of effector T cells and regulatory T cells (Treg)s using flow cytometry. Eight color flow cytometry analysis will be performed on the isolated mononuclear cells using the following antibodies: florescence conjugated anti-CD3, anti-CD4, anti-CD8, anti-CD25, anti-CD127, anti-Foxp3, anti-granzyme B and anti-perforin (BD Bioscience or eBioscience). For extracellular staining, cells will be incubated for 30 minutes at 4°C with optimal dilution of each antibody. Intracellular staining for Foxp3, granzyme B and perforin will be preceded by fixation and permeabilization with intracellular staining kit (eBioscience). Flow cytometry will be performed on a FACS LSRFortessa (BD) and analyzed using CellQuest software (BD). The results of flowcytometry pre and post treatment will be correlated with the clinical efficacy to identify possible mechanisms of tumor response

### 13. Appendix

#### APPENDIX A: CYP3A Inhibitors

Inhibitors of CYP3A are defined as follows. A comprehensive list of inhibitors can be found at the following website: <http://medicine.iupui.edu/clinpharm/ddis/table.aspx>. The general categorization into strong, moderate, and weak inhibitors according to the website is displayed below. Refer to Section 5.2 on instructions for concomitant use of CYP3A inhibitors and inducers with ibrutinib.

Inhibitors of CYP3A	Inducers of CYP3A
Strong inhibitors:	Carbamazepine
INDINAVIR	Efavirenz
NELFINAVIR	Nevirapine
RITONAVIR	Barbiturates
CLARITHROMYCIN	Glucocorticoids
ITRACONAZOLE	Modafinil
KETOCONAZOLE	Oxcarbazepine
NEFAZODONE	Phenobarbital
SAQUINAVIR	Phenytoin
SUBOXONE	Pioglitazone
TELITHROMYCIN	Rifabutin
Moderate inhibitors:	Rifampin
Aprepitant	St. John's Wort
Erythromycin	Troglitazone
diltiazem	
Fluconazole	
grapefruit juice	
Seville orange juice	
Verapamil	
Weak inhibitors:	
Cimetidine	
All other inhibitors:	
Amiodarone	
NOT azithromycin	
Chloramphenicol	
Boceprevir	
Ciprofloxacin	
Delaviridine	
diethyl-dithiocarbamate	
Fluvoxamine	
Gestodene	
Imatinib	
Mibefradil	
Mifepristone	
Norfloxacin	
Norfluoxetine	
star fruit	
Telaprevir	
Troleandomycin	
Voriconazole	

Source: <http://medicine.iupui.edu/clinpharm/ddis/table.aspx>.

## **APPENDIX B: RECIST Criteria for Measuring Tumor Response Antitumor Effect**

Response and progression will be evaluated in this study using the new international criteria proposed by the revised Response Evaluation Criteria in Solid Tumors (RECIST) guideline (version 1.1) (Eisenhauer et al., 2009). Changes in the largest diameter (unidimensional measurement) of the tumor lesions and the shortest diameter in the case of malignant lymph nodes are used in the RECIST criteria.

### **Definitions**

**Evaluable for toxicity.** All patients will be evaluable for toxicity from the time of their first treatment with ibrutinib or pembrolizumab.

**Evaluable for objective response.** Only those patients who have measurable disease present at baseline, have received at least one cycle of therapy, and have had their disease re-evaluated will be considered evaluable for response. These patients will have their response classified according to the definitions stated below. (Note: Patients who exhibit objective disease progression prior to the end of cycle 1 will also be considered evaluable.)

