#### **4.3.1 Screen Failures/Dropouts/Replacements**

A subject who discontinues study participation prematurely for any reasons except death, disease progression and severe toxicity is defined as a dropout. A subject who, for any reason (e.g., failure to satisfy the selection criteria), terminates the study before the time point used for the definition of “dropout” (see above) is regarded a “screening failure”. Subjects who withdraw from treatment (for any reason) during dose seeking phase may be replaced. Patients will be

considered inevaluable for the primary endpoint of disease control rate if they do not have at least one post-baseline disease response assessment. Inevaluable patients may be replaced.

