### 9.3 Analysis Sets

All subjects who receive at least one dose of the study medication will be included in the safety evaluation.

All subjects who undergo at least one staging reassessment will be used for efficacy evaluations.

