## 9.6 Calculation or derivation of tumor response variables

At each visit subjects will be programmatically assigned a RECIST and irRC visit response of CR, PR, SD or PD depending on the status of their disease compared to baseline and previous assessments. See Appendix B.

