### **Tumor response**

Tumor response data will be summarized for dosed subjects with measurable disease at baseline.

Objective response rate, disease control rate and PFS will be summarized in the expansion phase arm.

Tumor response will be analyzed using RECIST 1.1 criteria (Appendix B) and the immune response criteria. Confirmation of immune response will be done at the discretion of the investigator.

In this classification, the overall response is determined as follows:

- Immune response CR (irCR) is a complete disappearance of all lesions (whether measurable or not, and no new lesions) with confirmation by a repeat, consecutive assessment no less than 4 weeks from the first documentation.
- Immune response PR (irPR) is a decrease in tumor burden of greater than or equal to 50% relative to baseline. This must be confirmed by a consecutive assessment at least 4 weeks after the first documentation.
- Immune response SD (irSD) is classified as those who do not meet criteria for irCR or irPR and who do not have irPD
- Immune response PD (irPD) is an increase in tumor burden of greater than or equal to 25% relative to the minimum recorded tumor burden which must be confirmed by a repeat, consecutive assessment no less than 4 weeks from the first documentation.

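### Appendix B classifies response only after an undefined minimum of one cycle, which conflicts with 4.3.1, 9.3 and 9.7, is likely to inflate the objective response rate, and leaves open whether the disease control set is restricted too

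*Combined protocol and SAP*

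**What the plan says.** Four places in the combined protocol and SAP say who counts for efficacy.

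- **Appendix B, Definitions (evaluable for objective response).** Patients must have measurable disease at baseline and must "have received at least one cycle of therapy, and have had their disease re-evaluated will be considered evaluable for response". Classification attaches to that group: "These patients will have their response classified according to the definitions stated below". The one exception is a note: "Patients who exhibit objective disease progression prior to the end of cycle 1 will also be considered evaluable".
- **Section 4.3.1.** Patients are "considered inevaluable for the primary endpoint of disease control rate if they do not have at least one post-baseline disease response assessment". The same section adds: "Inevaluable patients may be replaced".
- **Section 9.3.** "All subjects who undergo at least one staging reassessment will be used for efficacy evaluations".
- **Section 9.7, Tumor response.** "Tumor response data will be summarized for dosed subjects with measurable disease at baseline".

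Section 9.6 assigns the visit categories CR, PR, SD and PD "depending on the status of their disease compared to baseline and previous assessments. See Appendix B". Section 9.7 also cites Appendix B for the RECIST criteria, and lists objective response, disease control and PFS together under tumour response.

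**The concern.** Only Appendix B sets a minimum exposure, and nothing says which rule prevails. What counts as having received one cycle is not defined. Section 5.1 makes a cycle three weeks long, with pembrolizumab every three weeks and ibrutinib daily. It is therefore unclear whether a patient who was infused on day 1 and stopped ibrutinib in week 2 has received a cycle.

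The exception is one-sided. It keeps patients who progress during cycle 1 but not those who stop for toxicity. Whether a patient gets through the first cycle is itself a result of treatment, so the Appendix B set selects on an outcome. In an open-label, single-arm trial judged against fixed rates, the denominator should be settled before any data are seen.

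**Working it through.** **1. One patient under each rule.** Take a patient with measurable disease who stops both drugs in week 2 for toxicity and is rescanned at about day 43, the start of cycle 3, when section 6.4 places the first scheduled scan.

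| Rule | Counted? |
|---|---|
| 4.3.1 (disease control) | Yes: has a post-baseline assessment |
| 9.3 (efficacy evaluations) | Yes: has been restaged |
| 9.7 (tumour response) | Yes: dosed, measurable disease |
| Appendix B | No, if one cycle means a completed cycle |

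The Appendix B answer is the same whether that scan shows SD or PD. Had progression been documented before the end of cycle 1, the exception would have kept the patient.

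**2. Objective response.** Let f be the share of treated patients dropped. If none of them has a CR or PR, the reported rate is the true rate times 1/(1 − f). The documents do not give f, so a range is assumed on a base of 36 treated patients (32/0.9 = 35.6, rounded up):

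- 1 of 36: 36/35 = 1.03
- 2 of 36: 36/34 = 1.06
- 4 of 36: 36/32 = 1.13

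Without replacement, 4 responders in 32 (12.5%) would be reported as 4 of 30 (13.3%) if two are dropped, or 4 of 29 (13.8%) if three are.

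**3. Disease control: the plan's own design first.** Section 9.2 gives 18 patients in stage 1, continuing with at least 1 success, and 32 in total, effective with at least 4. The benchmarks are 5% and 20%, with both error rates set at 0.10. With X ~ Bin(18, p) and Y ~ Bin(14, p),

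P(effective) = Σ over x ≥ 1 of P(X = x) · P(Y ≥ 4 − x).

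At p = 0.05:

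- x = 1: 0.37631 × 0.03005 = 0.01131
- x = 2: 0.16835 × 0.15299 = 0.02575
- x = 3: 0.04726 × 0.51233 = 0.02421
- x ≥ 4: 0.01087

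The sum is 0.072. At p = 0.20 the same formula gives 0.901. An exhaustive minimax search returns this same design, so the plan's figures reproduce.

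**4. Disease control if Appendix B were applied to it (illustration only).** Suppose a share f is dropped and replaced, and the dropped patients have disease control rate d. The rate among those counted is then q = (p − f·d)/(1 − f). At a true p of 0.05:

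| Dropped | d | q | P(effective) |
|---|---|---|---|
| none | – | 0.0500 | 0.072 |
| 1 of 36 | 0 | 0.0514 | 0.078 |
| 2 of 36 | 0 | 0.0529 | 0.085 |
| 4 of 36 | 0 | 0.0563 | 0.101 |
| 2 of 36 | 0.05 | 0.0500 | 0.072 |
| 2 of 36 | 0.10 | 0.0471 | 0.060 |

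The bias is upward if the dropped patients do worse than the rest, nil if they do the same, and downward if they do better.

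**The case against.** The strongest reply is that the primary endpoint is already protected. The Appendix B definition is headed for objective response, whereas 4.3.1 gives a separate, explicit rule for the disease control rate, and 9.3 agrees with it. The reference in 9.6 can be read as pointing to the category definitions and not to an analysis set. This largely stands. A reader might infer that the clause inflates the primary disease control rate and erodes the type I error, but the documents do not establish that. It would take someone applying the Appendix B set in place of 4.3.1. What remains is that 9.6 and 9.7 leave this possible: disease control is built from Appendix B categories, and Appendix B limits who is classified.

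The direction for disease control is also open. Early stoppers without progression may have SD, which counts as control if it still holds at 4 months.

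The affected group is narrow. The first scheduled scan is at cycle 3, and section 6.5 makes the end-of-treatment scan permissive. Many cycle 1 stoppers would have no rescan and already fall out under 4.3.1 and 9.3, which is a separate matter. It is therefore tempting, but not supported, to take the synopsis's 10% attrition as the size of the effect: its causes are not stated, and it is not a rate of stopping in cycle 1.

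Finally, a reader might take the rule to require a full cycle. That is one reading of an undefined term. None of this removes the conflict between Appendix B and 9.7 for objective response.

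**Conclusion.** The conflict is real and can be checked from the text alone. For objective response, the Appendix B rule selects on tolerating early treatment. It is likely to inflate the rate, because a CR or PR is unlikely after less than one cycle. The size is modest: a factor of 1.03 to 1.13 if 1 to 4 of 36 are dropped, assuming all are non-responders and that receiving one cycle means completing it.

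For the primary disease control rate, the finding is an ambiguity and not a demonstrated bias. The probabilities in the last table show what could happen if the Appendix B set were used. They do not estimate what will happen.

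**What to change.** - **Appendix B:** delete the one-cycle condition and the cycle 1 note. State that every dosed patient with a post-baseline assessment is classified by that assessment, however much treatment was received.
- **Objective response:** use the 9.7 denominator (dosed patients with measurable disease) and count patients without a documented CR or PR as non-responders.
- **Sections 9.3 and 9.6:** state that the Appendix B evaluability definition does not restrict the disease control rate set.
- **Optional:** keep the one-cycle set as a labelled sensitivity analysis, with receipt of one cycle defined.

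The cost is a few sentences of wording. No new patients or data are needed and no treatment rule changes. The downside is a slightly lower reported response rate. This change does not settle how treated patients with no scan at all count for 4-month disease control.

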### **Disease Parameters**

**Measurable disease.** Measurable lesions are defined as those that can be accurately measured in at least one dimension (longest diameter to be recorded) as  $\geq 10$  mm with CT scan, MRI or calipers by clinical exam. All tumor measurements must be recorded in millimeters (or decimal fractions of centimeters).

Note: Tumor lesions that are situated in a previously irradiated area might be considered measurable if the lesion has increased in size since the radiation.

**Malignant lymph nodes.** To be considered pathologically enlarged and measurable, a lymph node must be  $\geq 15$  mm in short axis when assessed by CT scan (CT scan slice thickness recommended to be no greater than 5 mm). At baseline and in follow-up, only the short axis will be measured and followed.

**Non-measurable disease.** All other lesions (or sites of disease), including small lesions (longest diameter  $< 10$  mm or pathological lymph nodes with  $\geq 10$  to  $< 15$  mm short axis), are considered non-measurable disease. Bone lesions, leptomeningeal disease, ascites, pleural/pericardial effusions, lymphangitis cutis/pulmonitis, and abdominal masses (not followed by CT or MRI), are considered as non-measurable.

**Target lesions.** All measurable lesions up to a maximum of 2 lesions per organ and 5 lesions in total, representative of all involved organs, should be identified as **target lesions** and recorded and measured at baseline. Target lesions should be selected on the basis of their size (lesions with the longest diameter), be representative of all involved organs, but in addition should be those that lend themselves to reproducible repeated measurements. It may be the case that, on occasion, the largest lesion does not lend itself to reproducible measurement in

which circumstance the next largest lesion which can be measured reproducibly should be selected. A sum of the diameters (longest for non-nodal lesions, short axis for nodal lesions) for all target lesions will be calculated and reported as the baseline sum diameters. If lymph nodes are to be included in the sum, then only the short axis is added into the sum. The baseline sum diameters will be used as reference to further characterize any objective tumor regression in the measurable dimension of the disease.

**Non-target lesions.** All other lesions (or sites of disease) including any measurable lesions over and above the 5 target lesions should be identified as **non-target lesions** and should also be recorded at baseline. Measurements of these lesions are not required, but the presence, absence, or in rare cases unequivocal progression of each should be noted throughout follow-up.

